Statistical Analysis Plan (SAP)

TRIAL FULL TITLE	A new interdisciplinary collaboration structure in secondary and primary care to improve medication safety in the elderly (IMMENSE study) – a randomized controlled trial
Protocol	https://bmjopen.bmj.com/content/8/1/e020106
PVO NUMBER	41366 The Norwegian Centre for Research Data and the Norwegian Data Protection Authority
SAP VERSION	1.0
CLINICAL TRIAL NUMBER	NCT02816086
SAP VERSION DATE	2021-03-18
TRIAL STATISTICIAN	[name]
TRIAL CHIEF INVESTIGATOR	[name]
SAP AUTHORS	[name], [name], [name] and [name]

This SAP will concern the statistical analysis on the primary and secondary endpoints of the main article of the intervention study. Some secondary endpoints mentioned in the protocol article is excluded and will be presented in future SAPs.

SAP Signatures

I give my approval for the attached SAP entitled “A new interdisciplinary collaboration structure in secondary and primary care to improve medication safety in the elderly (IMMENSE study) – a randomized controlled trial” dated xx.xx.2020

Chief Investigator

Name: [name]

Signature: 

Date: 18.03.2021

Statistician

Name: [name]

Signature: 

Date: 18.03.2021

Abbreviations

CCI	Charlson Comorbidity Index
ED	Emergency Department
EQ5D-VAS	EuroQoL 5L - health-related quality of life
GP	General practitioner
HRQoL	Health related quality of life
MMS	Mini-mental Status
SAP	Statistical Analysis Plan
TILT	No; Tidlig Identifisering av Livstruende Tilstander Eng; Early Identification of Life-threatening Conditions.

Definitions

An “acute readmission” is defined as when a patient unplanned has been formally admitted to a hospital ward, independent whether the patient was visiting the ED before hospitalization.

An “ED visit”, is defined as when a patient unplanned have been visiting the ED (including both the ED run by the municipality and the ED run by the hospital) but not formally admitted to the hospital. If the patient is admitted to hospital following an ED visit, it will be defined as a readmission.

This non-blinded randomized controlled trial investigates whether an interdisciplinary intervention in geriatric patients (>70y) admitted to hospital will impact patient outcomes. The intervention is a new inter-professional collaboration structure between hospital physician, pharmacists and GPs focusing on medications applying the Integrated Medicines Management (IMM) methodology. The novelty is the inclusion of the clinical pharmacist in the team, who performs medication reconciliation, medication review, ensures correct communication about medications to patients and primary care and follows up with primary care after discharge. The study includes patients from two hospital sites; a geriatric ward at the University Hospital of North Norway (UNN) Tromsø and a general internal medicines ward at UNN, Harstad (1).

Following in the document, amendments from the published protocol will be pinpointed and ambiguities in the protocol descriptions will be clarified, see grey boxes.

2. Study Objectives and Endpoints

2.1 Objectives

The primary objective is to investigate the effects of the intervention on rate of emergency medical visits (acute readmissions and visits to emergency departments (EDs)) 12 months after hospital discharge.

Secondary objectives include to investigate the effects on:

- Acute readmissions
- Length of index hospital stay
- Time to first readmission
- 30-day readmissions
- Mortality rate

Specification:

- Regarding the primary objective, “Rate of emergency medical visits” is referring to the number of emergency medical visits per patient included in the trial.
- Regarding the secondary objectives, some that are described in the original published protocol will not be described in this SAP, but in SAPs for follow-up studies (see section 2.3).

2.2 Primary endpoint

The primary outcome is the rate of ‘acute readmissions and ED visits’ 12 months after discharge from the index hospital stay in the intervention group compared with the control group. An acute readmission is defined as any subsequent admission following the index admission excluding elective readmissions.

Specification:

- This is a composite endpoint combining “Acute readmissions” and “ED visits”.
- We count all events per patient during 12 months from the index stay.

2.3 Secondary endpoints

Statistical analysis plan will be presented in this SAP only for the following secondary endpoints:

- Length of index hospital stay
- Time to first acute readmission after discharge from index hospital stay (12 months follow-up)
- The proportion of patients with acute readmissions within 30 days of discharge
- Mortality rate during 12 months' follow-up

Specification:

Some of the secondary endpoints from the protocol have been excluded from this SAP and will be presented in SAPs for follow-up studies.

3. Methods

3.1 General Study Design and Plan

We will recruit eligible participants to the study when they are admitted to the geriatric internal medicines ward (hereby called geriatric ward) in Tromsø or the general internal medicines ward (hereby called medicine ward) in Harstad. Participants will be randomized into two study arms, intervention and control (standard care) in a 1:1 relationship, stratifying on study site only. Randomization is performed after eligibility has been confirmed and patients have consented to participate. Consecutively, the intervention is commenced.

Study progress:

- The study started including patients in Tromsø on 22. September 2016
- The study started including patients in Harstad on March 2017
- Inclusion stopped in December 2019 in both study sites. The last patient was discharged from hospital on 22. December 2019
- Patients are followed-up for 12 months after discharge, and data will be collected after December 2020

3.2 Inclusion-Exclusion Criteria and General Study Population

Eligible patients were all patients aged ≥ 70 years admitted acutely to one of the study departments, independent of disease status, medication use, or whether they were able to consent.

Patients admitted to the intervention wards were included if they were willing to provide written informed consent during hospital stay (patient or next of kin).

Patients were excluded from the study if they met one of the following exclusion criteria:

- admitted to the study ward more than 72 hours before evaluation of eligibility
- moved to and discharged from other wards during the index stay
- unable to understand Norwegian (patient or next of kin)
- considered terminally ill or with a short life expectancy
- planned discharged on the inclusion day
- occupying a bed in a study ward but under the care of physicians from a non-study ward
- intervention from a study pharmacist considered necessary for ethical reasons (before randomization or in control group)

3.3 Randomisation and Blinding

Patients were randomized into intervention group and control group in a 1:1 relationship, only stratifying on study site. We applied block randomization with concealed and permuted randomization block sizes. The web-based randomization program was supplied by Unit for Applied Clinical Research, Faculty of Medicine Norwegian University of Science and Technology, Trondheim, which is an independent collaboration partner not involved in the project. Blinding was not feasible in this study, as everybody knew whether or not the intervention was delivered.

3.4 Sample Size

No data on hospitalization rates or visits to ED exist from our hospital. Therefore, data from a similar study in Sweden was applied as basis for sample size calculations. Gillespie et al. found a 16% reduction in visits to the hospital. In 12 months, patients in the intervention group had on average 1.5 visits and the intervention group 1.7 visits (2). If we expect a rate of 1.7 acute hospital visits per year in our control group, we would need a total of 456 patients to show a 16% reduction in hospital visits with a significance level of 5% and a power of 80% (Poisson regression). To compensate for dropout, we aimed to include 250 patients in each study group.

4 General Considerations

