6.1 General on statistics

We will investigate data for normality and apply the appropriate statistical tests. A two-sided 5% significance level will be applied, with no adjustments for multiplicity.

All analyses will be performed applying SPSS for windows or Mac. P-values < 0.05 will be regarded as statistically significant. P-values ≥ 0.001 will be reported to 3 decimal places; p-values less than 0.001 will be reported as "<0.001". The mean, standard deviation, and any other statistics other than quantiles, will be reported to one decimal place greater than the original data. Quantiles, such as median, or minimum and maximum will use the same number of decimal places as the original data. Estimated parameters, not on the same scale as raw observations (e.g. regression coefficients) will be reported to 3 significant figures.

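### The stated 456 patients give about 64% power, not 80%, for a 16% reduction from 1.7 visits, and the source means quoted beside it imply about 12%

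*SAP*

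**What the plan says.** Section 3.4 (Sample Size) takes its assumptions from a Swedish study, which it says "found a 16% reduction in visits to the hospital". It gives that study's 12-month means as follows: "patients in the intervention group had on average 1.5 visits and the intervention group 1.7 visits". Both means carry the same group label.

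The calculation then starts from "If we expect a rate of 1.7 acute hospital visits per year in our control group" and concludes that the trial needs "a total of 456 patients to show a 16% reduction in hospital visits with a significance level of 5% and a power of 80" per cent, naming Poisson regression as the method. The target was raised to 250 per group to cover dropout. No allowance for overdispersion is mentioned.

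Section 6.1 settles the sidedness: "A two-sided 5% significance level will be applied, with no adjustments for multiplicity". Sections 3.1 and 3.3 give 1:1 allocation, and section 2.2 counts all events over 12 months.

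**The concern.** A 16% reduction from 1.7 is a difference of 0.272 visits per patient. With 228 patients per arm, the Poisson standard error of the log rate ratio is about 0.075, so the expected effect is only about 2.3 standard errors from zero. Two-sided 5% testing with 80% power needs about 2.8. The stated size therefore looks too small for the stated power.

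The source line raises a second doubt, because 1.5 against 1.7 is not a 16% reduction at face value.

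The figure concerns the primary endpoint. Readers use planned power to judge a non-significant result. If 80% is taken at face value, such a result would count more heavily against a 16% effect than the design allows, since the trial had at least about a one-in-three chance of missing that effect.

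**Working it through.** **Inputs (all from the SAP).** Control rate 1.7 per year (3.4); 16% reduction, so an intervention rate of 1.7 × 0.84 = 1.428 (3.4); 80% power (3.4); two-sided 5% (6.1); 1:1 allocation (3.3), so 456 is 228 per arm; one full year per patient (2.2); Poisson variance (3.4).

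**1. Attempt to reproduce 456.** For a Wald test on the log rate ratio:

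n per arm = (1.960 + 0.842)² × (1/1.7 + 1/1.428) / (ln 0.84)² = 7.849 × 1.2885 / 0.03040 = 332.7, which rounds up to 333, or 666 in total.

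Other standard formulas with the same inputs:

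- Rate difference: 7.849 × (1.7 + 1.428) / 0.272² = 331.8 per arm, 664 in total.
- Square-root transform: 7.849 × 0.5 / (√1.7 − √1.428)² = 331.2 per arm, 664 in total.
- Poisson-regression formula with separate null and alternative variances: (1.960 × 2 + 0.842 × √(2 + 2/0.84))² / (1.7 × (ln 0.84)²) = 625 in total.

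The range is 625 to 666. The stated 456 is 73% of the lowest figure and 68% of the highest.

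**2. Variants that might explain 456.**

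- One-sided 5%, 80% power: 494 to 526 by the Poisson formulas, and about 478 by the crudest approximations.
- Intervention rate rounded to 1.4: 506 to 544 two-sided. One-sided, it is 400 to 428.
- 1.7 taken as the intervention rate (control 2.02) with a one-sided test: 442.
- 456 read as per arm: power would be 90.7%.
- One-sided 5% with 75% power: 456.0 before rounding to whole arms.
- Rate ratio of about 0.81 (a 19% reduction), two-sided, 80% power: about 456.
- Control rate of about 2.48 with a 16% reduction, two-sided, 80% power: about 456.

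Each variant that lands on 456 changes at least one input that the SAP states.

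**3. Power at the stated size.** The standard error at 228 per arm is √(1.2885/228) = 0.0752. Power = Φ(0.1744/0.0752 − 1.960) = Φ(0.359) = 0.640. At 250 per arm the standard error is 0.0718 and power is Φ(0.469) = 0.680. Simulation of Poisson counts at 228 per arm (400,000 runs) gives 0.642. At 333 per arm, simulation returns 0.802, so the method behaves as it should.

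**4. Detectable effect.** For 80% two-sided power under Poisson variance, the smallest reduction is 19.2% with 456 patients and 18.3% with 500.

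**5. The source line.** 1 − 1.5/1.7 = 11.8%. If both means were rounded to one decimal, the reduction could lie between 1 − 1.55/1.65 = 6.1% and 1 − 1.45/1.75 = 17.1%. For 1.7 against 1.5, power is 39% with 456 and 42% with 500, and 80% power needs about 1,258 patients.

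**6. Sensitivity to overdispersion.** The SAP gives no variance-to-mean ratio. The ratios above 1 are assumptions, and the variance is multiplied by the ratio.

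| Ratio | Power for 16%, 456 patients | Power for 16%, 500 patients |
|---|---|---|
| 1 (Poisson) | 64% | 68% |
| 1.5 | 47% | 51% |
| 2 | 37% | 40% |
| 3 | 27% | 29% |

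At ratio 2 with 500 patients, the reduction detectable with 80% power is about 25%.

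**The case against.** The arithmetic in steps 1 and 3 is not in dispute. The objections concern scope and weight.

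- **The source line may not be an error.** The 16% and the two means come from an outside study. The percentage could be an adjusted or differently defined estimate, and rounding alone allows up to about 17%. The calculation uses 1.7 and 16%, not 1.5, so the 39% and 42% figures describe a scenario the SAP did not plan for. This stands: the mismatch is an inconsistency as printed, to be clarified, and secondary to the power error.
- **The repeated group label is a slip.** The next sentence assigns 1.7 to controls, so nothing in the analysis turns on it. This stands.
- **The dispersion ratios are assumed.** True. They show the direction and possible size of the loss, and are not evidence of an arithmetic error.
- **Lost person-time may already be counted.** Section 6.3 subtracts hospital days and time after death, but the source figure is mean visits per patient over 12 months and may already reflect both. The documents do not settle this, so no power loss is claimed for it here.
- **Nothing downstream uses the 80%.** Recruitment ended in December 2019, and no test, population or decision rule depends on the figure. This is true, and it is why the remedy is limited to wording. It does not make the stated power correct.

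**Conclusion.** The concern holds. On the SAP's own inputs, 456 patients give about 64% power for a 16% reduction, and the full 500 at most about 68%. The stated 80% would have needed 625 to 666 patients, and the choice among standard formulas does not close that gap. These figures rest on Poisson variance, a full year of follow-up, 1:1 allocation and a two-sided 5% test. Overdispersion would lower the power by an amount the documents do not allow one to fix.

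The printed source rates and the printed percentage disagree (11.8% against 16%), but neither is shown to be wrong.

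**What to change.** Do not change the sample size; inclusion is closed. In section 3.4:

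1. Replace the power statement. Under Poisson assumptions and a two-sided 5% test, 456 and 500 patients give about 64% and 68% power for a 16% reduction from 1.7. Equivalently, they give 80% power for reductions of about 19% and 18%. If 456 rested on an input not stated, give that input and explain how it fits with section 6.1.
2. Add the lower power under overdispersion, for example at ratios of 1.5 to 3, labelled as assumed.
3. Make the source line consistent: identify the control group, and either align the means with the 16% or say how that percentage was defined.
4. State that a non-significant primary result will be interpreted from the confidence interval for the rate ratio, not from the planned power.

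The cost is wording in the SAP and the report, and a less favourable stated power. The SAP is dated 18 March 2021 and section 4.1 expects the analyses in May-June 2021, so the correction fits before results are known.

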4.1 Timing of Analyses

The analyses of the endpoints specified in section 2.3 will be performed when 12 months follow-up data for all patients have been received, anticipated during May-June 2021.

4.2 Analysis Populations

Full Analysis Population: All patients included in the study and not withdrawing their consent, regardless of whether they were excluded after randomization.

Per Protocol Population: The full analysis population, except those who were excluded after randomisation.

Assigning patients to full analysis and per protocol population will be conducted before data on the primary endpoint is collected.

4.3 Variables, data sources and subgroups

Variables will be collected at the following time points during the study:

- 1) at baseline (during index hospitalization)
- 2) after follow-up from the following national registries:
 - Norwegian Patient Registry (NPR) (hospitalizations and ED visits)
 - The Norwegian Health Economics Administration Registry (ED visits)
 - The National Cause of Death Registry (time and cause of deaths)

See Appendix 1 for details on the variables.

Variables that may influence on the primary endpoint will be investigated for interactions.

Subgroups

The following subgroups will be analysed for different treatment effects:

1. Number of medications at admission and discharge
2. Age groups 70–79, 80–89 and 90+
3. Patient responsibility for own medication management at discharge
4. Number and types of comorbidities at discharge
5. Number of hospital visits prior to inclusion

6. Length of index hospital stay
7. Referral from home, homecare or nursing home
8. Able to self-provide informed consent
9. Differences between study sites

Specification:

We have added one subgroup (No 9 differences between study sites) which originally was not described in the published protocol.

4.4 Missing Data

We do not expect missing data for the primary endpoint as our national health registries are complete. When data is missing in independent variables, results will be presented with specified total number of patients contributing to each variable. In addition, for dependent and independent variables with more than 5% missing data, multiple imputation will be considered. Results of raw and imputed data will be presented.

4.5 Multi-centre Studies

The study sites in Tromsø and Harstad will be analysed together, but a subgroup analysis will be performed to investigate a possible centre effect. Regarding the intervention, the procedures, guidelines and working tools have been similar in both study sites and patients in the two study sites have been treated similarly. The only exception is with regard to collection of health-related quality of life. For this variable at baseline, all patients at study site Harstad were interviewed over telephone while for the Tromsø population, the first measurement was performed face-to-face.

4.6 Multiple Testing

To account for multiplicity, we will perform confirmatory significance testing for primary and secondary outcomes. All other significant tests will be treated as hypothesis generating. As we have conducted an RCT, we assume that any difference in baseline data is introduced by chance.

5 Summary of Study Data

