6.3 Primary endpoint analysis

The composite endpoint

The primary endpoint is defined as the composite endpoint “acute readmission and ED visits” 12 months after discharge from the index hospital stay in the intervention group compared with the control group. Consequently, the endpoint comprises both “readmissions” and “visit to emergency departments (ED)”.

Hypothesis

- The H0 hypothesis is: The intervention does not influence the number of primary endpoints during 12 months after index hospitalization.
- The H1 hypothesis is: The intervention influences the number of primary endpoints during 12 months after index hospitalization.

Figure 6.2 illustrates how we assume that the endpoint will occur during the follow-up time.

[figure not shown]

Figure 6.2: Illustrations of primary endpoints during a 12-month follow-up time for patients in the two groups, assuming that we will see a difference between the groups.

- a) Number of patients having 1-x number of endpoints during the 12-month follow-up period.
- b) Cumulative number of endpoints (in total) 1-12 months after index hospital discharge.

Person-time (time under risk for experiencing an endpoint) contribution

Each patient may experience many endpoints during the 12-month follow-up, and the primary endpoint per patient will be related to the patient’s person-time contribution during the 12-month follow-up period after index hospital discharge.

To account for that a new endpoint cannot occur in the period a patient is “in an endpoint” (i.e. time in hospital if patient is hospitalised), and that patients may die before the end of the 12-month follow-up period, we will calculate person-time contribution for all patients, which is “time outside hospital” in the follow-up period where the person is still alive. Consequently, total person time contribution per patient =

365 days follow-up time after hospital discharge, minus “time in an endpoint” minus time after (potential) death.

Primary endpoint analysis

Specification

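### Section 4.6 makes the primary and four secondary endpoints confirmatory as its answer to multiplicity, but section 6.1 tests each at an unadjusted 5%, so error across the five is not controlled

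*SAP*

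**What the plan says.** Two sections of the SAP speak to multiplicity.

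- Section 4.6 gives the approach: "To account for multiplicity, we will perform confirmatory significance testing for primary and secondary outcomes". It sets these outcomes apart from everything else: "All other significant tests will be treated as hypothesis generating".
- Section 6.1 gives the level: "A two-sided 5% significance level will be applied, with no adjustments for multiplicity". It adds the decision rule: "P-values < 0.05 will be regarded as statistically significant".

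The endpoints concerned are one primary, of which section 2.2 says "This is a composite endpoint combining “Acute readmissions” and “ED visits", and the secondaries introduced in section 2.3 by "Statistical analysis plan will be presented in this SAP only for the following secondary endpoints". Four follow: length of the index stay, time to first acute readmission, acute readmission within 30 days, and mortality over 12 months. Table 6.1 has the same four rows.

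Neither section, nor the endpoint analyses in 6.3 and 6.4, gives a testing order, a condition on the primary result, a split of alpha or an adjustment procedure.

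**The concern.** Section 4.6 offers the confirmatory status of five endpoints as the means of dealing with multiplicity. Testing several endpoints as confirmatory is what raises the multiplicity question, and section 6.1 then says that nothing is adjusted. Leaving secondary endpoints unadjusted is acceptable practice when they are presented as supportive. The difficulty is the combination of the confirmatory label with an unadjusted 5% for each.

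What is at stake is the wording of claims in the main article. Suppose the primary comparison is not significant and one secondary, for example mortality, falls just below 0.05. Under 6.1 that result is significant, and under 4.6 it belongs to the confirmatory set. Nothing in the SAP stops it from being reported as a confirmed effect, although it is one of five tests that could have produced such a claim.

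**Working it through.** **Inputs from the SAP**

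- Level per test: 0.05, two-sided, unadjusted (section 6.1).
- Confirmatory endpoints: 1 primary (section 2.2) + 4 secondaries (section 2.3, Table 6.1) = 5, counting one test per endpoint.
- Correlation between the five test statistics: not given, so assumed, with a range shown.

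The SAP states no family-wise error rate. There is therefore no figure of its own to reproduce beyond the 5% per test.

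**Step 1: what section 4.6 does and does not do.** It assigns all other tests, including the nine subgroup analyses of section 4.3, to hypothesis generation. They leave the confirmatory family. Within the family of five, each endpoint keeps its full 5%.

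**Step 2: independent tests, no true effect on any endpoint.**

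1 − (1 − 0.05)^5 = 1 − 0.7738 = 0.226, or 22.6%.

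**Step 3: bound without an independence assumption.** The sum of the individual levels is 5 × 0.05 = 0.25, so the rate cannot exceed 25%.

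**Step 4: positive correlation.** Independence is not realistic here. Readmissions are part of the composite (section 6.3), and two secondaries are built from the same events. Simulating five jointly normal test statistics with equal correlation (400,000 draws, all nulls true, two-sided 5% each) gives:

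| Assumed correlation | At least one false claim |
|---|---|
| 0 | 22.6% |
| 0.2 | 21.8% |
| 0.3 | 20.9% |
| 0.5 | 18.4% |
| 0.7 | 14.9% |
| 0.9 | 10.2% |

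An assumed pattern with correlations of 0.4 to 0.6 among the three readmission-based endpoints and 0.05 to 0.2 elsewhere gives 20.5%.

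**Step 5: the secondaries alone.** If the intervention affects none of the four secondaries, the chance of at least one false secondary claim is 1 − 0.95^4 = 18.5% if independent, and at most 4 × 0.05 = 20%, whatever the truth about the primary.

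**Step 6: sensitivity to the count.** Section 2.1 begins its list with "Secondary objectives include to investigate the effects on" and names five items. The additional one is acute readmissions, which has no row in section 2.3 or Table 6.1. If it were also tested as confirmatory, the family would be six: 1 − 0.95^6 = 26.5% if independent.

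**Step 7: the error rate after the change.** With only the primary confirmatory, the confirmatory type I error is 5%. With the secondaries tested by Holm only after a significant primary, there are two cases. If the primary null is true, any false claim first requires a false rejection of the primary, which has probability at most 5%. If the primary effect is real, Holm holds the error among the four secondaries at 5% or less. The family-wise rate is therefore at most 5% in both cases.

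**The case against.** The best defence is that the two sections can be read together. Section 4.6 nowhere promises a family-wise error of 5%. It limits how many tests may carry a confirmatory claim, and section 6.1 then openly discloses that p-values are not adjusted. On this reading multiplicity is handled by restricting the family, and the restriction is a real one, since it removes the subgroup and interaction tests.

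Part of this stands. The plan conceals nothing, and the restriction has value. A reader might infer from 4.6 that the plan asserts strong control at 5%; the text does not go that far. But the restriction does nothing among the five endpoints left in the family. Section 4.6 contrasts the secondary outcomes with the hypothesis-generating tests, so they cannot be read as merely supportive. An approach introduced as accounting for multiplicity and then left unadjusted within its own family still has to be reconciled.

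It can also be said that 4.6 does not state that a significant secondary would rescue a failed primary. That is correct. The plan has no such rule; it simply has nothing that prevents the claim.

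**Conclusion.** The point holds as an inconsistency between sections 4.6 and 6.1, with an uncontrolled error rate across the five endpoints called confirmatory. With all nulls true and one test per endpoint, the chance of at least one false confirmatory claim is about 23% if the tests are independent, at most 25%, and roughly 15% to 22% under assumed equal correlations of 0.7 to 0.2. Even at an assumed 0.9 it is about twice 5%, so the conclusion does not depend on independence.

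Two stronger readings are tempting and are not supported:

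- A reader might take 23% as the plan's actual family-wise error. That figure needs five independent tests, and three of the five endpoints share readmission events. The SAP gives no correlations, so only a range can be stated.
- A reader might take the figure as the chance of a false main result. There is one primary endpoint, tested at two-sided 5%, and its type I error stays at 5% whatever is done with the secondaries.

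This should be corrected before the analysis. It bears on what may be claimed for the secondary endpoints and does not threaten the primary comparison.

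**What to change.** Reword sections 4.6 and 6.1 so that they agree and only the primary endpoint is confirmatory, at two-sided 5%. Then choose one of two routes for the four secondaries:

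- **(a) Supportive.** Report each as an estimate with a 95% confidence interval and a nominal p-value, labelled supportive. The statement in 6.1 that nothing is adjusted can then stay.
- **(b) Confirmatory after the primary.** Test the secondaries only if the primary is significant, either with Holm adjustment (smallest p-value against 0.05/4 = 0.0125, and so on) or in an order fixed in the SAP. Amend 6.1 to match. If the primary is not significant, report them as in (a).

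Either route resolves the conflict; (a) is the simpler. Under (b) the SAP should also say whether acute readmissions, listed in section 2.1 only, belongs to the family.

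The cost is SAP wording, with no new data and no change of design. The SAP is dated 18 March 2021 and section 4.1 expects the analyses in May to June 2021, so the timetable leaves room to settle the text before group allocation is revealed. The downside is that a secondary endpoint can no longer be called confirmed on an unadjusted p < 0.05.
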